# **DOCUMENT REVISION HISTORY PAGE**

Document Number:	Rev:	Page:	
90D0167	О	2 of 32	

Title: Ambulatory Remote Patient Monitoring using the μCor Heart Failure and Arrhythmia Management System (PATCH)Feasibility Study: Protocol

Revision History Of Document					
CO Rev Number	Description of Change	Author	Effective Date		
FI NA	First version	RP	7/17/17		
A NA	Changed the device name from Continuous Mobile Cardiac Telemetry System to uCor Heart Failure and Arrhythmia Management System.	RP	8/22/17		
B NA	
 
The following changes were made:         
 
Removed CE-mark reference for the device
 
Subjects no longer have to send photographs of the skin and device placement. Instead, they will note their skin condition and device location on the subject diary
 
Study coordinators will collect subject diaries once a week
 
Removed the requirement that phase II of the study can start only after completion of phase I
 
Updated the adverse event section per MEDDEV guidelines
 
Edits to improve the study implementation
 
 
 
	RP	10/16/17		
C NA	
 
The following changes were made:         
 
First monitoring report to be sent within 24 hours rather than 2 hours.
 
Devices that are worn for only the first 7 days will now be sent to the sponsor
 
End of use study visit will occur at 90 days or when subject decides to end the study.
 
In the Subject Diary, replaced AM/PM with the 24-hour clock numbers
 
In the Subject Diary, subjects now will record when they replace the patch
 
 
 
	RP	2/19/18		

ZOLL Services Form Number: 90A0001-A03 Form REV Level: FI

# **Study Summary**

	Ambulatory remote patient monitoring with the µCor Heart Failure and			
Title	Arrhythmia Management System (PATCH) feasibility study.			
Short Title	PATCH Feasibility Study			
ZOLL Protocol Number	90D0167			
Study Design	Prospective, non-interventional, feasibility study.			
Study Duration	8 months, from start of screening to finishing the study.			
Study Center(s)	Multi-center study, with a maximum of 8 centers in Europe.			
Primary Objective(s)	To observe the feasibility of remotely monitoring patients with the novel $\mu$ Cor Heart Failure and Arrhythmia Management System ( $\mu$ Cor system) that non-invasively captures thoracic fluid content, electrocardiogram, heart rate, respiratory rate, activity, and body posture.			
Study Population	Health adult volunteers (21 years or older) and adult patients with a clinical indication for ambulatory outpatient cardiac monitoring.			
Intervention	The study will consist of two phases. Phase I of the study will enroll 6 healthy volunteers, who have no indication for remote cardiac monitoring. Subjects are required to participate in the study for 30 days. Phase II of the study will enroll up to 44 patients indicated for outpatient cardiac monitoring and will participate in the study for up to 90 days. All subjects will wear the device in two locations, one along the left midaxillary line and the other along the left midclavicular line for the first seven days. Thereafter, for the remainder of the study, half the enrolled subjects will only wear the device in the left midclavicular position and the other half will wear the device in the left midaxillary position. Subjects will use a diary to keep a daily log their activities of daily living (phase I) or a log of any symptoms related to heart rhythm abnormalities and heart failure (phase II). Data will be acquired with the μCor system and wirelessly transmitted daily to a remote server for processing, generating thoracic fluid content, ECG, heart rate, respiration rate, activity, and posture measurements. Investigators will have access only to ECG data. Study staff will make weekly phone calls to subjects and record any new clinically actionable events. Patients will have monthly office visits. At the end of 30 days (phase I) or 90 days (phase II), patients will end wear and will complete the study follow-up questionnaire.			
Study Size	The study will enroll a maximum of 50 subjects. Six healthy volunteers will be enrolled for phase I of the study. Remaining 44 subjects will be enrolled for phase II and will have an indication of outpatient cardiac monitoring.			

#### 1 Introduction

This document is a protocol for a human research study. This study is to be conducted according to US and international standards of Good Clinical Practice (International Conference on Harmonization ICHE6).

#### 1.1 Background

Mobile cardiac telemetry (MCT) allows for ambulatory monitoring of electrocardiograph (ECG) signal continuously. When a cardiac event occurs, the MCT system instantaneously transmits the data to a monitoring center, where the data is analyzed live and a report is sent to the patient's physician for diagnosis and therapy management. Previous studies have shown that use of MCT, instead of a Holter or event monitor, leads to better outcomes with regard to diagnostic yield, management of arrhythmias through the use antiarrhythmic drugs, and cost savings in the hospital for cardiac procedures. 4

Given the patient management capabilities of the MCT system, ZOLL has developed a novel radiofrequency (RF) based  $\mu\text{Cor}$  Heart Failure and Arrhythmia Management System ( $\mu\text{Cor}$  system). The system records ECG and heart rate through 2 electrodes and respiration rate, activity, and posture through a tri-axial accelerometer. Thoracic impedance, a measure of lung fluid, is estimated using low-power electromagnetic pulses at radio frequencies of 0.5-2.5GHz. The  $\mu\text{Cor}$  system continuously records and transmits ECG and accelerometer data to the monitoring center. RF data are recorded periodically according to a predefined schedule. Physiological parameters such as thoracic impedance, heart rate, respiration rate, activity, and posture are extracted from the recorded data by dedicated software at the monitoring center. Certified technicians at the monitoring center review received data and prepare clinical reports to the prescribing physician. Because the  $\mu\text{Cor}$  system has not yet been tested in a real-world setting, the purpose of this study is to observe the feasibility of the novel  $\mu\text{Cor}$  system to remotely monitor patients in a real-world, ambulatory setting.

#### 1.2 Preclinical Data

NA

#### 1.3 Clinical Data to Date

NA

#### 1.4 Study Device

#### 1.4.1 System Components

The µCor System consists of the following components:

- A) Patch
- B) Sensor
- C) Charger
- D) Data transmission device (Gateway)
- E) Server

Once activated, the wearable Sensor automatically acquires ECG, thoracic impedance, Heart Rate, Respiration Rate, Activity, and Posture measurements. Patients can also activate a patient trigger when they experience symptoms such as palpitations, shortness

of breath, or lightheadedness by double tapping the Sensor when it is on the body. Data are automatically transmitted from the Sensor to the Data transmission device, and from there to the Server for analysis (see Fig. 1). Certified technicians at the Monitoring Center review the data generated by the Server and prepare reports according to the pre-defined criteria as requested by the prescribing physician. Data provided in the report will aid the prescribing physicians in the diagnosis and identification of various clinical conditions, events and/or trends. The  $\mu Cor$  System is designed for use in outpatient clinic and home settings.

[figure not shown]

Figure 1: Data transmission of the μCor System

#### 1.4.2 Patch

The Patch (Fig. 2) consists of a plastic frame intended for housing the Sensor, and two ECG electrodes on each side of the frame. It is applied to your body.

The Patch is a single-use, disposable item. At the end of 5 days, it should be replaced with a new Patch.

[figure not shown]

Figure 2: Patch

#### 1.4.3 Sensor

The Sensor (Fig. 3) is a battery powered unit that acquires data. The Sensor connects to the Patch via the snap-in clip and positioning tabs. Through the adhesive backing on the Patch, the device becomes wearable. The Sensor is not disposable and needs to be returned to ZOLL upon the completion of the prescription. A light indicator is located close to the center and serves to communicate the Sensor's status at different points of use. Note that the light indicator is visible only when lit.

Figure 2: Sensor's front view

#### 1.4.4 Charger

A dedicated Charger (Fig 4) is supplied with the  $\mu$ Cor System for recharging the Sensor and the Data Transmission Device. A blue light appears when the Charger is connected to an AC outlet.

Figure 4: Charger

#### 1.4.5 Data transmission device (Gateway)

A Data Transmission Device or Gateway is responsible for sending data from the Sensor to the Server for data analysis. When the screen display is on, the gateway battery status is visible on the screen. Once the battery status is under a certain level, a short beeping sound will be made every few minutes until the battery is depleted or the Gateway is placed in the Charger.

[figure not shown]

Figure 5: Gateway

#### 1.4.6 Server

The Server refers to the hardware and the processing software and resides in a remote cyber-secure location. The software analyzes the data received from the Sensor via the Gateway and processes the data into clinical values for presentation to your healthcare provider after review by certified technicians at the Monitoring Center.

#### 1.4.7 Device (Sensor +Patch) Placement Location

There are two locations for device (Sensor + Patch) placement: (1) along the left midaxillary line in line with the nipple (side location) and (2) along the left midclavicular line, above the nipple and below clavicle.

[figure not shown]

Figure 6: Device (Sensor + Patch) placement location

#### 2 Study Objectives

#### 2.1 Primary Objective(s)

The primary objective of this study is to observe the feasibility of the novel  $\mu$ Cor system to remotely monitor patients. Feasibility will be assessed in terms of:

- 2.1.1 Logistics of equipping patients with the  $\mu$ Cor system in the physician's office. This will include verifying that the system is able to transmit data to a remote server and that a monitoring report is received by the physician's office.
- 2.1.2 Subject's ability to wear the device for the specified time period of up to 90 days.
- 2.1.3 Subject's ability to place the device in the correct anatomical position during every reapplication, as described in the patient instructions for use. Device placement case report forms and daily device data signal quality will be used to track the accuracy of device placement and repeatability.
- 2.1.4 Ability of the system to transmit data daily to the remote servers for processing.
- 2.1.5 Ability to provide a timely arrhythmia monitoring (daily, episodic, and end of monitoring) reports to physicians.
- 2.1.6 Documenting the following clinically actionable events in an outpatient setting via weekly phone calls to the subject:
  - 2.1.6.1 Emergency room visits
  - 2.1.6.2 Unplanned physician visits
  - 2.1.6.3 New arrhythmia and heart failure (HF) symptoms
  - 2.1.6.4 All-cause and HF hospitalizations
  - 2.1.6.5 Alterations and additions in HF and cardiac medications
  - 2.1.6.6 All-cause and cardiovascular mortality at 90 days

#### 2.2 Secondary Objective(s)

A number of **secondary objectives** will be evaluated and these will include:

- 2.2.1 Equivalency of data recorded by the device placed along the left midaxillary line versus the data recoded by the device placed along the left midclavicular line.
- 2.2.2 Correlation between detected heart rhythm abnormalities and any clinically actionable events.
- 2.2.3 Correlation between detected thoracic fluid content changes and any clinically actionable events.

Page 7 of 27

ZOLL Document Number: 90D0167 PATCH Feasibility Study

Version: C

- 2.2.4 Correlation between changes in thoracic fluid content and/or detected heart rhythm abnormalities with all-cause and cardiovascular mortality.
- 2.2.5 Short term (days), mid-term (weeks), and long-term (months) stability of the device recorded data in the same patient.
- 2.2.6 Stability of the device recorded data with multiple reapplications of the μCor system.

#### 2.3 Safety Objective(s)

To document the number and severity of serious adverse events and adverse events related to use of the  $\mu$ Cor system.

[figure not shown]
#### 2.4 Additional Objective(s)

NA

#### 3 Study Design

### 3.1 General Design

A) Phase I

ZOLL Document Number: 90D0167 PATCH Feasibility Study

Version: C

#### B) Phase II

[figure not shown]

Figure 2: Schematic of trial design with various phases of the study.

This is a multicenter, prospective, non-interventional, feasibility study. A maximum of 8 centers in Europe will participate in the study. Phase I of the study will enroll 6 healthy volunteers, who have no indication for remote monitoring. Subjects are required to participate in the study for 30 days. For the first seven days, all subjects will wear the  $\mu Cor$  system in two locations, one along the left midaxillary line and the other along the left midclavicular line. Thereafter, for the remainder of the study period (23 days), 3 subjects will wear the device in the midclavicular position and the remaining 3 subjects will wear the device in the midaxillary position. Data will be acquired with the  $\mu Cor$  system and wirelessly transmitted daily to a remote server for processing. Subjects will keep a diary to record their daily activities of living, their skin condition due to use of the  $\mu Cor$  device/s, and placement location of the device/s. (Appendix A). In addition, the subjects will receive weekly phone calls to ensure that the device is performing as intended. Furthermore, the study staff will ask the subject send their diaries after each week of wear to the study coordinator. At the end of 30 days, these subjects will end wear and will complete study follow-up questionnaire.

For phase II of the study, up to 44 patients eligible for remote monitoring will receive a  $\mu$ Cor system after they are enrolled in the study. Subjects must be willing to wear the  $\mu$ Cor system continuously for 90 days. In case of adverse skin reaction to the  $\mu$ Cor adhesive and/or electrodes, on the discretion of physician, subjects may discontinue wearing the device for up to 72 hours. All subjects will wear the device in two locations, one along the left midaxillary line and the other along the left midclavicular line for the first seven days. Thereafter, for the remainder of the study, half the enrolled subjects will only wear the device in the left midclavicular position and the other half will wear the device in the left midaxillary

position. Subjects will use a diary to keep a daily log of their daily activities of living, any symptoms related to heart rhythm abnormalities and heart failure, their skin condition due to use of the  $\mu$ Cor device/s, and the placement location of the device/s (Appendix A). Data will be acquired with the  $\mu$ Cor system and wirelessly transmitted daily to a remote server for processing, generating thoracic fluid content, ECG, heart rate, respiration rate, activity, and posture measurements. Investigators will have access only to ECG data. Study staff will make weekly phone calls to subjects and record any new clinical actionable events. Furthermore, the study staff will ask the subject send their diaries after each week of wear to the study coordinator. Patients will have monthly office visits. At the end of the participation period (anticipated 90 days), patients will end wear and will complete the study follow-up questionnaire.

#### 3.2 Primary Study Endpoints

Only observational data will be collected to assess the feasibility of implementing the  $\mu$ Cor system to monitor patients in an outpatient setting. There are no target objectives associated with these data; however, these endpoints will be assessed:

- 3.2.1 Logistics that captures device placement, subject training, device data transmission, and monitoring report receipt during the initial device fitting at the physician's office.
- 3.2.2 Total number of days the device is worn and wear time per day.
- 3.2.3 Accuracy and repeatability of device placement during the anticipated 90 day wear period.
- 3.2.4 Number of data transmissions from the device to the remote severs during the study period.
- 3.2.5 Timing of the monitoring reports to physicians.
- 3.2.6 Weekly documentation of skin condition.
- 3.2.7 Timely documentation of clinically actionable events.

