#### 5.4 Early Withdrawal of Subjects

#### 5.4.1 When and How to Withdraw Subjects

Subjects may voluntarily withdraw participation at point during the study period. In addition, subjects will be withdrawn from the study prior to study completion under following scenarios:

- 5.4.1.1 Skin irritation and/or rash due to use of the  $\mu$ Cor device that prevents subjects from wearing the device for longer than 72 hours.
- 5.4.1.2 Any life-threatening condition that prevents subjects from participating in the study for longer than 7 days.
- 5.4.1.3 Subjects no longer meeting the inclusion/exclusion criteria.

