#### 6.2 Scheduled Visits

#### 6.2.1 Visit 1: Screening and fitting of the μCor system

- 6.2.1.1 For phase I of the study, healthy volunteers will be screened. For phase II, a chart review of patients will be used to evaluate patients for enrollment. A screening log will be maintained.
- 6.2.1.2 Informed consent will be obtained on eligible patients who wish to participate in the study.
- 6.2.1.3 The initial clinical and demographic data will be recorded. This may be done by chart review.
- 6.2.1.4 Subjects will be trained on care and use of the  $\mu$ Cor system per the Instructions for Use manual.
- 6.2.1.5 Each site will sequentially assign a number to each subject as they are enrolled, starting at 001.
- 6.2.1.6 Subjects will be then fitted, per the Instructions for Use manual, with two μCor systems, one along the left midaxillary line and the other along the left midclavicular line. Subjects will wear the two devices for first seven days. After that, subjects with an odd number will be assigned to wear the device only

Page 13 of 27

ZOLL Document Number: 90D0167 PATCH Feasibility Study

Version: C

along the midaxillary line and those with an even number will wear the device only along midclavicular line.

- 6.2.1.7 A confirmation e-mail will be sent to the designated study staff within 1 hour of fitting and activating the devices that the  $\mu$ Cor system is able to transmit data to a remote server.
- 6.2.1.8 First monitoring report will be sent the physician-investigator or designated study staff within 24 hours of fitting and activating the devices.

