#### 6.2.2 Visit 2: Wear period from 0 to 7 days

Subjects will wear two µCor devices for the first 7 days. All subjects will keep a diary to record their daily activities of living, their skin condition due to use of the µCor device/s, and the placement location of the device (Appendix A). For subjects participating in phase II of the study they will keep a dairy to record any symptoms related to heart rhythm abnormalities and heart failure (Appendix A). Symptoms associated with transient arrhythmias include syncope, near syncope, dizziness, palpitation, shortness of breath, chest discomfort, weakness, and diaphoresis. Symptoms of heart failure include: dyspnea, fatigue and weakness, edema, persistent coughing or wheezing, lack of appetite and nausea, confusion and impaired thinking, and increased heart rate. Arrhythmia monitoring reports will be provided to the physician when an actionable arrhythmia is detected per the notification specified by the physician-investigator. On day 7, the study coordinator will call the subjects to record any clinical actionable events and check on status of the device. During the call, subjects will be requested to send to send their dairy every week to the study coordinator. In addition, the study coordinator will remind the subjects to remove one of the devices, midaxillary or midclavicular, depending on whether the subjects are assigned an odd or even number. Subjects will also be instructed on how to send one of the study devices back to the sponsor.

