# **Symptoms**

Please circle any of the following symptoms that you are experiencing. If possible, note the time when the symptoms started and duration.

Racing heartbeat	Slow heartbeat	Flutter in yo	ur chest	Chest pain	
Shortness of breath	Lightheadedness o	r dizziness	Sweating	Near fainting	Time:
Fatigue Swelling	of feet, ankles, legs,	or abdomen	Other:		Duration:
Racing heartbeat	Slow heartbeat	Flutter in yo	ur chest	Chest pain	
Shortness of breath	Lightheadedness o	r dizziness	Sweating	Near fainting	Time:
Fatigue Swelling	of feet, ankles, legs,	or abdomen	Other:		Duration:
Racing heartbeat	Slow heartbeat	Flutter in yo	ur chest	Chest pain	
Shortness of breath	Lightheadedness o	r dizziness	Sweating	Near fainting	Time:
Fatigue Swelling	of feet, ankles, legs,	or abdomen	Other:		Duration:
	-				

ZOLL Document Number: 90D0167 PATCH Feasibility Study

area

Page 26 of 27

Version: C

[figure not shown]
DATE		Sun Mon Tue Wed Thu Fri Sat	
Skin Con	dition rea	ease rate the skin condition under the $\mu$ Cor patch adhesive. Do this be applying the new patch. Provide the skin condition rating for each device location) that you are wearing.	
		Front Location	
Date and	I Time of patch re	eplacement:	
Please ra	ate the skin cond	ition in the following manner:	
1. G	Grade 0 (None): N	lo redness, rash, irritation, or itchiness	
2. G	Grade 1 (Mild): Re	edness	
	Ra	ish	
	Irri	tation	
	Itc	hiness	
	Grade 2 (Moderat eeling/scaling	e): Rash that breaks skin, hard or soft pimples or light	
	Grade 3 (Severe): rea	Blistering, open ulcers, wet peeling, serious rash over a la	arge
		Side Location	
Date and	I Time of patch re	eplacement:	
Please ra	ate the skin cond	ition in the following manner:	
1. G	Grade 0 (None): N	lo redness, rash, irritation, or itchiness	
5. G	Grade 1 (Mild): Re	edness	
	Ra	sh	
	Irri	tation	
	Itc	hiness	
	Grade 2 (Moderat eeling/scaling	e): Rash that breaks skin, hard or soft pimples or light	

3. Grade 3 (Severe): Blistering, open ulcers, wet peeling, serious rash over a large

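### The diary prompts a skin grade when a new patch goes on, but nothing prompts one when a patch comes off and is not replaced, so the last patch at each site has no prompted grade

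*Combined protocol and SAP*

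**What the plan says.** - **Endpoint.** Item 3.2.6 of Section 3.2 is "Weekly documentation of skin condition". Section 12.1 lists skin condition among the data to be collected. Section 8.4 plans descriptive and qualitative analysis, and Section 8.6 marks missing-data handling as not applicable.
- **Instrument.** The only skin scale shown is the 0 to 3 grade in the Appendix A diary. Its instruction is damaged in the text available ("Do this be applying the new patch"). The natural reading is that the subject rates the skin before the new patch goes on. The form's date and time field for each location refers to patch replacement, which fits that reading. The instruction covers locations being worn: "applying the new patch. Provide the skin condition rating for each device".
- **Patch life.** Section 1.4.2: "At the end of 5 days, it should be replaced with a new Patch".
- **Day 7.** Section 6.2.1: "Subjects will wear the two devices for first seven days". Section 6.2.2 makes the day-7 contact a phone call at which "the study coordinator will remind the subjects to remove one of the devices, midaxillary or midclavicular". No skin rating is mentioned there.
- **Skin reactions.** Section 3.1 allows phase II subjects to pause wear for up to 72 hours at the physician's discretion. Section 5.4.1 withdraws a subject when irritation or rash "prevents subjects from wearing the device for longer than 72 hours".
- **End of wear.** Section 6.2.5 has the coordinator collect diaries, adverse events and the device. Table I in Section 6.5 has no row for skin assessment.
- **Frequency.** Section 3.1 describes the phase II diary as a daily log and lists skin condition among its contents. That is a third frequency, beside weekly in Section 3.2 and per replacement in Appendix A.

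**The concern.** A rating tied to putting on the next patch misses any patch that has no successor. Some of those patches are routine: the retired site at day 7 and the planned end of wear. Others have no successor because the skin reacted badly enough to stop wear. In that second group the missing grade depends on the outcome being measured.

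A related problem arises in a skin-related pause. The prompted grade belongs to the re-application step, by which time the skin may have partly recovered.

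At stake is the description of skin tolerance, which is part of the feasibility question for a device worn for up to 90 days. If the highest grades are the ones most often not prompted, a plain tabulation of diary grades may look milder than what subjects experienced. With missing-data handling marked as not applicable, the analysis plan would neither correct nor disclose this.

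**Working it through.** The plan gives no figure on this point to reproduce, so the check is a count of patches and prompted grades.

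**Inputs**
- Patch life: 5 days (Section 1.4.2).
- Two-site wear: 7 days, then one site is retired (Section 6.2.1).
- Phase I: 6 subjects, 30 days. Phase II: up to 44 subjects, 90 days (Sections 3.1 and 5.2).
- Assumptions: full compliance, changes exactly on schedule, no early loss of adhesion, and the form followed as written.

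**Formulas**
- Patches at a site = days of wear ÷ patch life, rounded up.
- Prompted grades at a site = patches − 1, because the last patch has no successor.

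**Per completer**

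| | Continuing site | Retired site | Total | No prompted grade |
|---|---|---|---|---|
| Phase II | 90/5 = 18 patches, 17 grades | 7/5, rounded up = 2 patches, 1 grade | 20 patches, 18 grades | 2 of 20 (10%) |
| Phase I | 30/5 = 6 patches, 5 grades | 2 patches, 1 grade | 8 patches, 6 grades | 2 of 8 (25%) |

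**All 50 subjects, if all complete**
- Patches: 44 × 20 + 6 × 8 = 880 + 48 = 928.
- Prompted grades: 44 × 18 + 6 × 6 = 792 + 36 = 828.
- Without a prompted grade: 928 − 828 = 100, and 100/928 = 10.8%.

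**Sensitivity to the change interval.** The count stays at 2 per subject, one per site, so it is 100 throughout. The share is 100/1530 = 6.5% with 3-day changes, 100/1160 = 8.6% with 4-day changes and 100/652 = 15.3% with 7-day changes.

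**Is the weekly frequency met?** In phase II, replacements at the continuing site fall on days 5, 10, …, 85. Counted by week they give 1, 1, 2, 1, 2, 1, 1, 2, 1, 2, 1, 1, 1, so each of the 13 weeks has at least one grade. The gap is the last patch, not the weekly count.

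**Wear ended by a skin reaction.** No new patch follows, so the patch in place at that moment has no prompted grade in any such case. The documents give no rate for this. If 5% to 15% of 44 patients stopped for this reason (purely an assumption), that would be 0.05 × 44 = 2.2 to 0.15 × 44 = 6.6, or about 2 to 7 patients.

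**After the fix.** Rating at every removal gives 20 of 20 (phase II), 8 of 8 (phase I) and 928 of 928 overall.

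**The case against.** A reader might infer that the last patch is never rated, or that a reaction that stops wear goes unrecorded. The documents do not support either inference, for these reasons:

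- **The body text is broader than the form.** Section 3.1 calls the phase II diary a daily log that includes skin condition, Sections 6.2.2 to 6.2.4 keep subjects recording throughout wear, and the Appendix A skin page carries a date and day-of-week header. The form also does not forbid a grade at other times. This stands against an absolute claim. It does not close the gap, because Section 3.1 points to Appendix A as the form, and that form names replacement as the moment to rate.
- **Adverse-event recording catches the event.** Section 10.1.1 lists skin irritation, rash, skin tearing and allergic reaction as anticipated device effects. Section 10.2.1 requires non-serious adverse device effects to be recorded and events to be followed up. Section 6.2.5 collects adverse events when a subject ends early. This stands: what may be missing is the grade, not the event. However, the minimum fields in Section 10.2.1 cover description, status, discontinuation and seriousness, without a severity grade, whereas the safety objective in Section 2.3 asks for severity.
- **Some forms are not available.** The CRFs and the follow-up questionnaire are not in the documents, so a skin item there cannot be ruled out. No section describes one.
- **The endpoint is descriptive.** There is no target or acceptance criterion, weekly grades are obtained at the continuing phase II site, and no worst-grade summary is planned. This limits the consequence to how skin tolerance is described. Earlier patches at the same site would also have been graded if the subject got past the first change.
- **The pause.** That the grade follows recovery is an inference from the form's timing. It may happen; it is not certain.

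**Conclusion.** The point holds in a limited form. As written, the form and visit schedule prompt no skin grade for the last patch at each site: 2 of 20 patches per phase II completer, 2 of 8 per phase I completer and 100 of 928 (10.8%) if all 50 subjects complete with 5-day changes. Most of these omissions would be routine. The important ones are patches removed because of a skin reaction, where the absence of a prompt is tied to severity. The distribution of grades for endpoint 3.2.6 may therefore lean towards mild. The documents give no rate of skin-related stopping, so the size of that lean cannot be stated, and a firm claim of bias would go too far. Separately, the daily, weekly and per-replacement frequencies disagree and must be reconciled. This is worth correcting, but it does not threaten the study.

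**What to change.** - Change the Appendix A instruction so that the skin is rated at every patch removal, whether or not a new patch follows. Name the day-7 removal, the start of any pause, withdrawal and end of wear.
- Add a removal date and time field for each location.
- Have the coordinator record the subject-reported grade at the day-7 call and the grade at the final visit, and add a skin row to Table I.
- Reconcile Sections 3.1 and 3.2 and Appendix A on one rating frequency.
- In Section 8.4, report the worst grade per subject and location alongside the adverse device effects.

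The cost is one diary sentence and one CRF line at contacts already scheduled, plus the matching wording edits. The change concerns measurement only and leaves the rules on pausing and withdrawal as they are.
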